## 5.3 ASSESSMENT OF SAFETY

### 5.3.1 Physical examination

A complete physical examination will be performed by the Investigator at the visits indicated in the Flow Chart. Documentation of the physical examination and any findings must be part of the source documents available at the site.

### 5.3.2 Vital Signs, body weight and height

Systolic and diastolic BP and Pulse Rate should be performed at the visits indicated in the Flow Chart. The testing should be performed after resting for at least five minutes. For each patient, all BP recordings should be made using the same type of instrument (i.e. manual BP recording vs. automatic digital vital signs monitor) on the same arm if possible. Weight should be measured at the visits indicated in the Flow Chart in order to calculate CrCl according to Cockcroft-Gault (see Section 5.3.3). Height should be measured at the screening visit.

### 5.3.3 Safety laboratory parameters

All blood samples can be taken in a fasting or non-fasting condition.

Blood samples for safety testing will be analysed at the local laboratory and results will be recorded in the CRF. Testing should be done at visits as specified in the Flow Chart. The tests to be performed are listed in Table 5.3.3: 1.

If medically indicated, laboratory parameters may be retested or followed-up on as unscheduled tests.

Table 5.3.3: 1 Safety laboratory parameters

Chemistry	Haematology
ALT (SGPT)	Erythrocytes
AST (SGOT)	Haemoglobin
Alkaline Phosphatase	Haematocrit
Bilirubin total, fractionated if increased	Platelet Count
GGT	WBC count
Creatinine	
CrCl**	

\*\* According to Cockcroft-Gault formula

## Pregnancy Testing

A pregnancy test will be performed locally on all women of child bearing potential at the visits as specified in the [Flow Chart](#). A urine test is acceptable, unless local regulations

demand a serum test to be performed.

In addition, women of child bearing potential will be supplied with pregnancy tests and will be instructed to perform pregnancy testing every 4 weeks when visits are more than 4 weeks apart.

### **Renal Function Measurements**

Renal function must be measured before enrolling a patient in the trial, and at visits as indicated in the [Flow Chart](#) (safety laboratory tests). CrCl will be calculated using the Cockcroft-Gault formula, as follows:

- For creatinine in  $\mu\text{Mol/L}$ :

$$\frac{(140 - \text{age [years]}) \times \text{weight [kg]} \times 1.23 (\times 0.85 \text{ if female})}{\text{serum creatinine } [\mu\text{Mol/L}]}$$

- For creatinine in  $\text{mg/dL}$ :

$$\frac{(140 - \text{age [years]}) \times \text{weight [kg]} (\times 0.85 \text{ if female})}{72 \times \text{serum creatinine } [\text{mg/dL}]}$$

### **5.3.4      Electrocardiogram**

12-lead ECGs (I, II, III, aVR, aVL, aVF, V1 - V6) will be performed using the site's own devices at the visits indicated in the Flow Chart. The ECGs must be evaluated by the Investigator or a designee immediately, for investigation or treatment if necessary.

### **5.3.5      Other safety parameters (safety endpoints)**

#### **5.3.5.1      Composite endpoint of new haemorrhagic brain lesion or worsening of the haemorrhagic component of a previous lesion**

The neuroimaging which established the diagnosis of CVT will be used as baseline value. The safety endpoint "new haemorrhagic brain lesion or worsening of the haemorrhagic component of a previous lesion" will be assessed by comparing repeated neuroimaging that is routinely performed if the patient has a neurological worsening during the trial, or at the EOT visit, to the baseline image. The comparing of images and the categorisation of the lesions (see below) will be done by the AC.

A separate MRI protocol will be provided as part of the ISF and should be followed for the EOT imaging.

In order to assess any worsening of previous lesions, haemorrhagic brain lesions at baseline and during treatment / at EOT will be categorised as indicated in Table [5.3.5.1: 1](#) below, according the definitions as recommended by Von Kummer et al [[P15-09432](#)]:

Table 5.3.5.1: 1      Categorisation of haemorrhagic brain lesions

Class	Type	Description
1		Haemorrhagic transformation of infarcted brain tissue
1a	HI-1*	Scattered small petechiae, no mass effect
1b	HI-2	Confluent petechiae, no mass effect
1c	PH-1*	Haematoma within infarcted tissue, occupying <30%, no substantive mass effect
2		Intracerebral haemorrhage within and beyond infarcted brain tissue
	PH-2	Haematoma occupying 30% or more of the infarcted tissue, with obvious mass effect
3		Intracerebral haemorrhage outside the infarcted brain tissue or intracranial-extracerebral haemorrhage
3a		Parenchymal haematoma remote from infarcted brain tissue
3b		Intraventricular haemorrhage
3c		Subarachnoid haemorrhage
3d		Subdural haemorrhage

\* HI: haemorrhagic infarction; PH: parenchymatous haematoma

Any new haemorrhagic brain lesion will be categorised as Class 3 (Intracerebral haemorrhage outside the infarcted brain tissue or intracranial-extracerebral haemorrhage).

If there is more than one haemorrhagic lesion present on imaging, the category of the most severe lesion is assigned.

### 5.3.5.2      Bleeding

All bleeding events that occur after signing of informed consent will be collected. Depending on the specific endpoint, events that occur after randomisation to trial medication or events that occur after first intake of trial medication will be part of the analysis of the bleeding events. See Section [7.3](#) for more details.

Patients should be carefully assessed for signs and symptoms of bleeding. Bleeding will be classified as major or minor. Major bleeds will be further sub-classified as fatal and other major bleeds. The location of the bleeding including the specific critical area or organ into which the bleeding occurred and whether or not it prolongs hospitalisation will be recorded. MBEs and CRNMBEs will be reviewed by the AC.

The following definitions are specified for bleeds:

**Definition of a major bleed**

Major bleeds will be defined according to the ISTH definition of a major bleed, as follows [R05-0344]:

- Symptomatic bleeding in a critical area or organ, such as intracranial, intraspinal, intraocular, retroperitoneal, intra-articular or pericardial, or intramuscular with compartment syndrome

and/or

- Bleeding associated with a reduction in haemoglobin of at least 2g/dL (1.24mmol/L) within 24 hours, or leading to transfusion of two or more units of blood or packed cells

and/or

- Fatal bleed

**Definition of a life-threatening bleed**

For the purpose of exclusion criterion 5, life-threatening bleeds are defined as follows:

- Symptomatic intracranial bleed

and/or

- reduction in haemoglobin of at least 5g/dL

and/or

- transfusion of at least four units of blood or packed cells, associated with hypotension requiring the use of i.v. inotropic agents

and/or

- necessitates surgical intervention.

**Definition of intracranial haemorrhage (ICH)**

ICH comprises the subtypes of intracerebral bleeds, subdural bleeds, epidural bleeds and subarachnoid bleeds and will be recorded.

**Definition of a fatal bleeding**

Fatal bleeding is defined as a bleeding event that the AC determines as the primary cause of death or contributing directly to death.

 A seizure associated with a new intracranial bleed will be considered a symptomatic bleeding in a critical organ.

 Bleeding should be overt and the haemoglobin drop should be considered to be due to and temporally related to the bleeding event.

### **Definition of a CRNMBE**

A CRNMBE is a clinically overt bleed that does not meet the criteria for a major bleed but prompts a clinical response, in that it leads to at least one of the following:

- A hospital admission (i.e. overnight stay in the hospital) for bleeding  
or
- A physician guided medical or surgical treatment for bleeding  
or
- A physician guided change, interruption or discontinuation of trial medication

### **Any bleed**

This is the sum of all major and non-major bleeds.

## **5.3.6 Assessment of adverse events**

### **5.3.6.1 Definitions of AEs**

#### **Adverse event (AE)**

An AE is defined as any untoward medical occurrence in a patient or clinical investigation subject administered a medicinal product and which does not necessarily have to have a causal relationship with this treatment.

An AE can therefore be any unfavourable and unintended sign (including an abnormal laboratory finding), symptom, or disease temporally associated with the use of a medicinal product, whether or not considered related to the medicinal product.

#### **Adverse reaction**

An adverse reaction is defined as a response to a medicinal product which is noxious and unintended. Response in this context means that a causal relationship between a medicinal product and an AE is at least a reasonable possibility. Adverse reactions may arise from use of the product within or outside the terms of the marketing authorisation or from occupational exposure. Conditions of use outside the marketing authorization include off-label use, overdose, misuse, abuse and medication errors.

#### **Serious adverse event (SAE)**

An SAE is defined as any AE which:

- results in death
- is life-threatening, this refers to an event in which the patient was at risk of death at the time of the event; it does not refer to an event that hypothetically might have caused death if more severe
- requires inpatient hospitalisation or
- prolongation of existing hospitalisation

 Interruption of trial medication (more than omitting one dose) due to the bleeding event.

Proprietary confidential information © 2017 Boehringer Ingelheim International GmbH or one or more of its affiliated companies

- results in persistent or significant disability or incapacity, or
- is a congenital anomaly / birth defect  
or
- is to be deemed serious for any other reason if it is an important medical event when based upon appropriate medical judgment which may jeopardise the patient and may require medical or surgical intervention to prevent one of the other outcomes listed in the above definitions. Examples of such events are intensive treatment in an emergency room or at home for allergic bronchospasm, blood dyscrasias or convulsions that do not result in hospitalisation or development of dependency or abuse.

Any suspected transmission via a medicinal product of an infectious agent is considered a serious adverse reaction.

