#### **4.1.1 Identity of BI investigational product and comparator product**

The investigational product dabigatran etexilate and the comparator warfarin will be supplied by Boehringer Ingelheim Pharma GmbH & Co. KG, Germany. For details see Table 4.1.1: 1 and Table 4.1.1: 2.

Table 4.1.1: 1                    Dabigatran etexilate (Investigational drug)

Substance	Dabigatran etexilate
Brand name	Pradaxa®
Pharmaceutical formulation	Capsule
Source	Boehringer Ingelheim Pharma GmbH & Co. KG, Germany
Unit strength	150 mg
Posology	1 capsule 150 mg b.i.d. (total daily dose 300 mg)
Route of administration	p.o.

The main excipients of the dabigatran capsule include tartaric acid, acacia, hypromellose, dimeticone, talc, and hydroxylpropyl cellulose, HPMC (hydroxylpropylmethylcellulose) capsule shell consisting of titanium dioxide (E171) FD&C Yellow 6/Sunset Yellow (E110), FD&C Blue 2 /Indigo Carmine (E132) hypromellose, carrageenan and potassium chloride.

Table 4.1.1: 2                    Warfarin (active comparator)

Substance	Warfarin
Pharmaceutical formulation	Tablet
Source	Teva UK Limited, UK
Unit strength	1 mg; 3 mg; 5 mg
Posology	As needed to maintain a target INR of 2.0- 3.0
Route of administration:	p.o.

For easy identification warfarin tablet strengths will have a different colour label.

Patients will in general take warfarin once daily (q.d.). The individual doses will be titrated as needed, without splitting of any tablet, to maintain a target INR of 2.0 - 3.0. INR controls in patients randomised to receive warfarin will be performed as described in Section [4.1.4](#) and the [Flow Chart](#).

Warfarin and dabigatran etexilate supplies will be managed using an IRT system.

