### Patient randomised to receive dabigatran etexilate

Patients randomised to dabigatran etexilate will start the trial medication on the day of randomisation if they are not on oral anticoagulation (VKA) or if the INR is  $<2.0$ . If a patient is still receiving parenteral therapy, the first dose (capsule) of dabigatran etexilate should be given 0-2 hours prior to the time that the next dose of the initial parenteral therapy would be due, or at the time of discontinuation in case of continuous treatment (e.g. i.v. UFH).

If the patient is on oral anticoagulation with a VKA for their CVT and the INR is  $\geq 2.0$ , trial medication can be dispensed but the patient will be instructed not to start it until notified.

The initial parenteral anticoagulation and VKA will be discontinued. Follow-up INRs will be performed in 1-3 day intervals until it falls below 2.0, at which time the patient will be instructed by telephone to start taking the trial medication.

Actual date and time of administration of the first dose of trial medication and in case of interruptions are to be recorded in the CRF.

Patients will take their dabigatran etexilate dose as scheduled for a period of 24 weeks.

Dabigatran etexilate capsules should be taken in the morning and in the evening (one at each time point), at approximately the same time every day with a full glass of water. The capsules must not be crushed, nor opened and can be taken with or without food. If dyspeptic symptoms occur, the Investigator should instruct the patient to take the medication together with food and/or should consider adding a proton pump-inhibitor to the concomitant therapy of the patients.

The interval between doses should be as close to 12 hours as possible. If a dose of dabigatran etexilate is missed for any reason, the forgotten dose may still be taken up to six hours prior to the next scheduled dose. From six hours prior to the next scheduled dose on, the "missed" dose should be omitted. A double dose to make up for missed individual doses must not be taken.

Any patient who decides to discontinue trial medication should be considered for a switch to an appropriate (non-study) anticoagulant according to local practice. For patients receiving dabigatran etexilate, continuation of trial medication for 2-3 days to assist bridging may be appropriate. For recommendations on how to switch from dabigatran etexilate to other anticoagulants see Appendix [10.2](#).

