###### Preoperative phase, Elective Surgery:

Physicians may consider the following information regarding dabigatran etexilate when patients need to undergo surgery or elective procedures. Provided that the patient has normal renal function, the onset of effect of dabigatran etexilate is within 1 hour of dosing and dabigatran has peak concentrations 2-3 hours after an oral dose. Steady state is reached within 2-3 days. Plasma levels of dabigatran at steady state will vary across the population and are particularly affected by renal function. Patients with renal dysfunction may have elevated concentrations of dabigatran due to longer half-lives of active drug (see Table [4.2.1.3: 1](#)). Serum creatinine should normally be checked 1-2 weeks before surgery and the CrCl should be calculated using the Cockcroft-Gault formula (Section [5.3.3](#)). Patients with a CrCl <30mL/min during the course of this study should not be receiving trial medication (see Section [3.3.4.1](#)).

The following is a guide to the discontinuation of dabigatran etexilate (under special consideration of the half-life of dabigatran etexilate depending on renal function) before surgery taking renal function and additional risk factors into account. In patients with normal renal function, discontinuation of two doses of dabigatran etexilate will decrease plasma levels to approximately 25% of steady state trough levels and discontinuation of four doses will decrease dabigatran plasma levels to approximately 5-10% of steady-state trough levels.

Table 4.2.1.3: 1      Recommendations on cessation of trial medication in relation to the timing of major surgery

Renal function (CrCl, mL/min)	Estimated half- life if on dabigatran etexilate	Stop study dabigatran etexilate before surgery	
		High Risk of bleeding	Standard Risk
≥80	~ 13 hours	2 days before	24h prior (2 doses)
≥50 to <80	~ 15 (12-18) hours	2-3 days before	1-2 days before
≥30 to <50	~18 (18-24) hours	4 days before	At least 2 days (>48 hours)
<30	~ 27 (>24) hours	>5 days before	2-5 days

 CrCl can be estimated using serum creatinine by the Cockcroft-Gault formula (see Section 5.3.3). Patients who develop CrCl <30mL/min during the course of the trial should have trial medication stopped (see Section 3.3.4.1).

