Patients who died during the trial before an EOT scan is made and patients for whom for other reasons no EOT or on-treatment scan is available or analysable will not be included in the analysis of number of patients with new intracranial haemorrhage or worsening of the haemorrhagic component of a previous lesion.

TSAP for BI Trial No: 1160.248 Page 11 of 30 Proprietary confidential information © 2018 Boehringer Ingelheim International GmbH or one or more of its affiliated companies

ISTH definition of a CRNMBE:

A CRNMBE is a clinically overt bleed that does not meet the criteria for an MBE but prompts a clinical response, in that it leads to at least one of the following:

A hospital admission (i.e overnight stay in the hospital) for bleeding •

or

A physician guided medical or surgical treatment for bleeding •

or

A physician guided change, interruption or discontinuation of trial medication •

 TSAP for BI Trial No: 1160.248
 Page 12 of 30

 Proprietary confidential information © 2018 Boehringer Ingelheim International GmbH or one or more of its affiliated companies

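### The interruption criterion for clinically relevant non-major bleeding is counted in doses, so a one-day hold qualifies on twice-daily dabigatran but not on once-daily warfarin, and the SAP omits the threshold

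*Protocol*

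**What the plan says.** Under Protocol 5.3.5.2, a CRNMBE is an overt bleed that is not major but "prompts a clinical response, in that it leads to at least one of the following": a hospital admission, physician-guided treatment, or a physician-guided change, interruption or discontinuation of trial medication. The footnote marker sits on the word interruption only. The footnote reads "Interruption of trial medication (more than omitting one dose) due to the bleeding event". It is printed at the foot of the page, below the start of the serious adverse event definition in 5.3.6.1, but it belongs to the CRNMBE definition.

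The dosing schedules are in Protocol 4.1.1: "1 capsule 150 mg b.i.d. (total daily dose 300 mg") for dabigatran, and "Patients will in general take warfarin once daily (q.d.)" for the comparator. Neither document adapts the threshold to the schedule.

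SAP 5.2.2 gives the same third criterion as "A physician guided change, interruption or discontinuation of trial medication", with no dose threshold in the text supplied.

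Both CRNMBE and the composite of major bleeding or CRNMBE are secondary safety endpoints (Protocol 5.1.2, SAP 5.2.2).

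**The concern.** An endpoint definition should classify the same clinical response in the same way in both arms. A threshold counted in doses does not do so when one drug is given twice as often as the other. The trial is open label (Protocol 4.1.5.1), and whether to hold medication for a minor bleed is left to the investigator (Protocol 4.2.1.2). Blinded adjudication does not help here, because the committee applies the definition and the asymmetry is inside it.

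Two of the five secondary safety endpoints are at stake. They are reported as counts and percentages with confidence intervals and no test, in arms planned at 60, so a few patients classified by schedule rather than by bleed could colour the reading. Protocol 2.3 expects fewer haemorrhages on dabigatran, so the bleeding comparison will receive attention.

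**Working it through.** **Inputs**

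- Threshold: more than one omitted dose, so at least 2 (footnote to Protocol 5.3.5.2).
- Dabigatran: 2 doses a day (Protocol 4.1.1). Protocol 4.1.4 says "The interval between doses should be as close to 12 hours as possible". Interval 12 h.
- Warfarin: in general 1 dose a day (Protocol 4.1.1). Interval 24 h.

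**Check on the conversion.** The pre-surgery table in Protocol 4.2.1.3 equates a day with two dabigatran doses: "24h prior (2 doses"). This agrees with 24 / 12 = 2.

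**Formula.** Doses omitted = hold length / dosing interval. The hold meets the interruption criterion if the number of whole doses omitted is greater than 1.

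| Hold | Dabigatran (÷ 12 h) | Qualifies | Warfarin (÷ 24 h) | Qualifies |
|---|---|---|---|---|
| 12 h | 1 | no | 0.5 | no |
| 24 h | 2 | yes | 1 | no |
| 36 h | 3 | yes | 1.5 | no |
| 48 h | 4 | yes | 2 | yes |

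The shortest qualifying hold is 2 × 12 = 24 h on dabigatran and 2 × 24 = 48 h on warfarin.

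**Under the SAP wording.** With no threshold, any physician-guided interruption counts. A 24 h hold then qualifies in both arms. The two wordings are alternatives: the asymmetry exists under the protocol text and not under the SAP text.

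**Under a common duration.** A 24 h hold counts in both arms if the rule is 24 h or longer, and in neither if it is longer than 24 h.

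**Size.** The documents give no rate of bleeds that would qualify only through a one-day hold. As an illustration on assumed rates, suppose 2%, 5% or 10% of 60 patients per arm had such a hold as their only qualifying feature. The interruption criterion would then count 60 × 0.02 = 1.2, 60 × 0.05 = 3 or 60 × 0.10 = 6 patients on dabigatran and none on warfarin. One patient in 60 is 1.7 percentage points. That is a unit conversion, not an estimate of bias, and the actual denominator is the treated set.

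**The other routes.** The same third criterion also counts a *change* of medication, with no threshold. Dabigatran has one fixed dose and one strength; warfarin is titrated with 1, 3 and 5 mg tablets (Protocol 4.1.1, 4.1.4). A warfarin adjustment ordered because of a bleed can therefore qualify by a route that fixed-dose dabigatran largely lacks. A one-day warfarin hold could also qualify through admission or treatment, or arguably as a change.

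**The case against.** The strongest reply concerns direction. A reader might infer that the rule inflates the dabigatran CRNMBE count relative to warfarin. The documents do not support that for the whole endpoint: the interruption criterion alone works against dabigatran, but the unrestricted change criterion works the other way, and nothing shows which dominates. This objection stands in full.

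A reader might also infer that the SAP has redefined the endpoint, or that the mismatch adds to the asymmetry. Neither follows. SAP Section 3 assumes familiarity with the protocol, Section 4 lists no change to CRNMBE, and the major-bleed definition in SAP 5.1 also leaves out the protocol's footnotes. The omission looks like abbreviation. What remains is that the two texts, read literally, classify a one-day warfarin hold differently, and the reader is not told which applies. The adjudication charter, which was not available, may settle it.

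Third, equal hours off drug need not mean equal loss of anticoagulation. Protocol 4.2.1.3 says omitting two dabigatran doses, with normal renal function, takes levels to roughly a quarter of steady-state trough; nothing comparable is given for warfarin. This stands as a caution. However, the criterion is meant to capture the physician's response to the bleed, not residual drug effect, and a common duration compares responses more evenly than a dose count.

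Finally, the stakes are modest. All analyses are descriptive, any bleeding is a companion endpoint free of the threshold, and SAP 7.3 already summarises interruption days and the frequency of interruptions for adverse events. That summary is not linked to individual bleeds, so it cannot show how CRNMBEs qualified.

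**Conclusion.** The point holds for the interruption criterion. Under the protocol wording, a physician-guided hold of about one day for a non-major bleed qualifies on dabigatran and not on warfarin, which needs about two days. This rests on warfarin being taken once daily, which the protocol states as the general case, and on the charter containing no further rule. Under the SAP wording the asymmetry is absent, so the documents need to be reconciled.

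The net direction of any bias on CRNMBE and on major bleeding or CRNMBE is uncertain, and its size cannot be derived. Because these endpoints count patients, a reclassified bleed matters only in a patient with no other qualifying event. The primary composite, major bleeding and any bleeding do not depend on the threshold. This is a worthwhile, inexpensive improvement to two secondary safety endpoints, not a flaw in the trial's main comparison.

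**What to change.** For endpoint classification only, and without altering any treatment instruction:

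1. State the interruption threshold as one duration, the same in both arms, with identical wording in Protocol 5.3.5.2, SAP 5.2.2 and the adjudication charter. Say explicitly whether a hold of exactly that length counts.
2. Add one table of patients with CRNMBE by qualifying criterion (admission, treatment, change, interruption, discontinuation) and arm, with patients who qualify by interruption or change alone shown separately. This shows what drives any difference, in either direction.

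The cost is a wording change, one extra table and slightly less comparability with trials that use a dose-based footnote.
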